Does RTX lower the CAS of the non-steroid responsive TAO-patients (NR-RTX), in comparison to NR-C, that continued with iv GC, and R-GC? Do the background variables differ between NR-RTX and NR-GC or R-GC? And lastly, does the QoL differ between the R-GC and the NR-RTX at given measuring points?

Material and Methods

Study design

The RTX-study is a non-randomized prospective study that covers patients with moderate-severe TAO with indication for treatment with iv GC. For this study, a control group (NR-C) will be created.

Patients with TAO are evaluated at Department of Ophthalmology at Sahlgrenska University Hospital/ Mölndal's and are asked for participation if eligible. Variables collected at each visit Clinical Activity Score (CAS), Quality of Life (QoL) through ThyPRO self-assessment questionnaire, biochemical tests (fT4, fT3, TSH, TRAb, liver function tests, fasting blood glucose), blood pressure and waist. An oral glucose tolerance test (OGTT) is performed at 12, 18, and 46 weeks, and a short adrenocorticotrophic hormone (ACTH) test at 12 and 46 weeks. Dual-energy x-ray absorptiometry (DXA) of the spine is conducted at 0 and 18 weeks.

All patients in the RTX-study start the 12-week scheme of iv GC at baseline. After four weeks of treatment, an evaluation of the treatment outcome is made. If the patients have improved their CAS score by ≥ 2 points, they are classified as responders to iv GC (R-GC) and continue their 12-week iv GC scheme. The remainder of the patients are classified as non-responders to the treatment with iv GC and are switched to 1000 mg iv RTX in week 5 and 7, combined with a weekly oral dose of 12.5 – 15 mg MTX (NR-RTX). The RTX is administered at the department of Rheumatology at Sahlgrenska University Hospital. All included patients have thereafter follow-up visits at week 12, 18, 32, 46 and 68 weeks after baseline.

At week 18 and at all follow-up timepoints thereafter, patients in R-GC group are evaluated for possible relapse. If a patient in R-GC has a CAS ≥ 4 points and CAS has worsened by ≥ 2 points compared to the value measured in the prior evaluation time-point, the patient is

considered having a relapse. Patients with relapse are randomized to either treatment with RTX and MTX or with *per oral* GC and MTX.

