All patients included in the study are assessed according to study protocol, but if DON is developed, the affected patient is treated outside the study protocol in order to follow DON treatment regimen. The patients with DON still have the same evaluation time points as the other patients in the study, but they are excluded from the comparisons between groups after the occurrence of DON.

From the group of patients with moderate – severe TAO with indication for treatment with iv GC that do not meet inclusion/exclusion criteria for the RTX-study or declined participation, a control group (NR-C) of non-responders will be created. As they are not included in the RTX study, they continue with their 12 weeks scheme of iv GC treatment.

Data collected at the follow-up timepoints: QoL, safety data and information on adverse events.

Study population

Inclusion criteria for the RTX study: man or woman between 18-70 years old, TAO with 7-point score system of CAS ≥ 4 (less than 3 months old), euthyroid for at least 6 weeks.

Exclusion criteria for the RTX study were: DON, ulcerative corneal involvement, previous treatment with steroids for TAO (except for prophylaxis for TAO in connection with RAI), previous treatment with RTX, positive Hepatitis B or C serology, obtained a living vaccine within 4 weeks prior RTX+MTX to evaluation, history of recurrent significant infection or history of recurrent bacterial infections, assessment by the investigator that the patient may not attend to the protocol, current pregnancy or lactation, significant cardiac disease, including significant or uncontrolled arrhythmia, previous active tuberculosis, bone marrow depression with leukopenia, thrombocytopenia or significant anaemia, allergy to the active substance or any other substance in the medications or murine proteins, active, severe infections (such as tuberculosis, sepsis or opportunistic infections), patients with severe immunosuppression, severe cardiac failure or severe uncontrolled heart disease.

The TAO patients not included in the RTX-study will be identified using the diagnosis-related group (DRG) registry according to the 10th revision (ICD-10) in VGR. In DRG, a combination of different codes was used (TAO [H06.2], Graves' disease [E05.0] and iv infusion [DT016]).

Efficacy variables

In the study, both patients' eyes are evaluated regarding CAS and the score of and any improvement of the worst eye was used.

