1 STUDY DETAILS

1.1 Study Objectives

- A. Do the background variables differ between NR-RTX and R-GC or NR-GC?
- B. Does RTX lower the CAS of the non-steroid responsive TAO-patients (NR-RTX), in comparison to NR-C, that continued with iv GC, and R-GC?

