3 STATISTICAL METHODOLOGY

Tests between groups will be made for the NR-RTX group and all of the other groups one at a time; R-GC and NR-C (where applicable).

For continuous variables Mann-Whitney U-test will be used for analyses between two groups. For dichotomous variables Fisher exact test will be used for test between two groups. For ordered categorical variables Mantel Haenszel Chi Square test will be used for test between two groups.

For all continuous variables Wilcoxon's Signed-Rank test will be used for within group analyses.

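### Within-group signed-rank tests on CAS are uninformative in R-GC (weeks 0 to 4) and biased towards a fall in NR-RTX (weeks 4 to 12), because the week-4 CAS defines both groups

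*SAP*

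**What the plan says.** SAP section 3 gives one general rule for all continuous variables, that the Wilcoxon "Signed-Rank test will be used for within group analyses". It exempts neither CAS nor any interval.

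The protocol (Study design) forms the groups from CAS at the four-week evaluation: "If the patients have improved their CAS score by ≥ 2 points, they are classified as responders to iv GC (R-GC"). For everyone else: "The remainder of the patients are classified as non-responders to the treatment with iv GC and are switched to 1000 mg iv RTX". Entry requires "TAO with 7-point score system of CAS ≥ 4", and CAS is taken from the worst eye.

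SAP 2.3.1 lists CAS, and its change from the previous timepoint, as primary. SAP 2.3.2 lists change from baseline as secondary. All three are worded as comparisons between treatment groups. Objective B in SAP 1.1 opens with "Does RTX lower the CAS of the non-steroid responsive TAO-patients (NR-RTX") and goes on to name NR-C and R-GC as the comparators.

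Neither document mentions regression to the mean or says how within-group p-values should be read.

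**The concern.** A signed-rank test of change assumes that, with no effect, changes are symmetric about zero. That fails when the group was selected on one of the two values being compared.

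- **R-GC, weeks 0 to 4.** The definition of the group fixes the sign of every change. The test can only report how many patients there are.
- **NR-RTX, weeks 4 to 12.** Patients whose week-4 score happened to read high are over-represented. Week 4 is also the last evaluation before RTX, so it is the reference for the first change after RTX. Part of any fall at week 12 is the score returning to its usual level.

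Continuing effect of four weeks of iv GC, the natural course of the disease, and the MTX given alongside RTX would all add to the same fall. A small p-value within NR-RTX could therefore be cited as showing that RTX lowers CAS when it shows no such thing.

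**Working it through.** The documents give no sample size, alpha or CAS measurement error (SAP 1.4 reports that no power calculation was made), so there is no figure of the plan's own to reproduce.

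**R-GC, weeks 0 to 4.** All n changes are negative, so the positive rank sum is 0. Exactly one of the 2^n sign patterns gives that value, and doubling for a two-sided test gives p = 2/2^n:

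- n=5: 2/32 = 0.0625
- n=6: 2/64 = 0.031
- n=8: 2/256 = 0.0078
- n=10: 2/1024 = 0.0020

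This needs no assumption about the drug or the distribution of CAS. With the tie-corrected normal approximation, and all changes equal, p is already 0.025 at n=5.

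**NR-RTX, weeks 4 to 12, with no true change.** This was simulated.

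Inputs from the documents: a 7-point CAS, entry at 4 or more, and non-response defined as a fall of less than 2. The 70–80% GC response rate in the protocol's Background was used for calibration.

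Assumed inputs: true CAS SD 1.0 with mean between 4.0 and 5.0; GC fall with mean 2.2 and SD 1.2, giving about 70% responders; independent visit error; scores rounded and limited to 0–7; true week-12 CAS equal to true week-4 CAS; two-sided 5% level. Results for the exact signed-rank test are approximate:

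| Visit error SD | Mean apparent fall | n=10 | n=15 | n=20 |
|---|---|---|---|---|
| 0.5 | 0.28 | 5–7% | 11–14% | 23–25% |
| 0.7 | 0.44 | 12% | 24% | 38% |
| 1.0 | 0.70 | up to 25% | up to 47% | up to 62% |

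The version of the test matters at small n. At error SD 0.5 and n=10 the normal approximation rejects about 15% of the time, against about 5% for the exact test. The SAP does not say which will be used.

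**Sensitivity.** A second model took baseline true CAS as normal with mean 4.5 and SD 1, and the GC effect as normal with SD 1. Again the exact test was used.

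- Mean GC effect 2.0 to 2.5 (68–81% responders at these error SDs): at error SD 0.5, rejection is 7–12% (n=10), 16–26% (n=15) and 26–42% (n=20). At error SD 1.0 it is 24–34%, 43–60% and 58–74%.
- Mean GC effect 1.0 (37% responders) and error SD 0.5: 1–7% for n=10 to 20, so essentially no inflation.
- No measurement error and no drift: 0%.
- No measurement error, mean GC effect 2.0, and a further true fall of 0.5 points after week 4 that is unrelated to RTX: 71% at n=10 and 98% at n=15.

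**Between-group check.** Two non-responder groups drawn from one population by the same week-4 rule were compared by Mann-Whitney on the week 4–12 change. Under the same null the test rejects 3.5–6.2% of the time across all scenarios with error SD of at least 0.5, which is about nominal.

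**The case against.** The strongest reply is that the SAP does not rest its conclusions on these tests. Objective B read in full is a between-group question, as is the protocol's primary aim, and every listed primary and secondary CAS variable is a between-group comparison. This stands. A reader might infer that the flaw invalidates the primary analysis or the NR-RTX versus NR-C contrast; the documents do not support that. (NR-RTX versus R-GC is also affected by the week-4 selection, but that is a separate matter from the within-group tests.)

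Second, the SAP names neither of the two tests examined here and does not classify CAS as continuous or ordered categorical. That is so. But it gives no within-group method for ordered variables, and a CAS change score fits most naturally under the general rule.

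Third, a reader might infer that the false-positive rate in NR-RTX is always several times 5%. It is not. With small error and about 10 patients the exact test stays close to nominal, and the inputs that set the size are not in the documents. Only the direction is certain once there is any measurement error.

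Fourth, NR-RTX versus NR-C does not isolate RTX either. NR-RTX also receives MTX, NR-C continues iv GC, and NR-C consists of patients who did not meet the RTX-study criteria or declined. Their entry CAS may differ, and then regression to the mean need not cancel. This also stands, and it limits what the remedy can deliver.

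**Conclusion.** The point holds for the supportive within-group CAS tests and should be fixed; it is not fatal to the plan. The R-GC week 0–4 result is arithmetic: with the exact test it is below 0.05 for any n of 6 or more and says nothing about treatment. The NR-RTX week 4–12 test is biased towards a fall. Under the main assumptions its rejection rate with no true change runs from about nominal (n=10, error SD 0.5) to about 62% (n=20, error SD 1.0). That range depends on assumed group sizes, CAS error and response rate, and on the exact form of the test. Drift unrelated to RTX would raise it further.

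**What to change.** In SAP section 3:

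1. State that within-group CAS changes are descriptive (estimate and 95% CI, no p-value) and are not evidence of a treatment effect.
2. Drop the within-group CAS test for R-GC from week 0 to week 4.
3. Show the NR-RTX change from week 4 beside the same change in NR-C, with NR-C classified by the same week-4 rule.
4. Base the conclusion on objective B on that between-group difference. Describe it as RTX plus MTX versus continued iv GC in a non-randomised comparison, and note that regression to the mean cancels only if entry CAS is similar in the two groups.

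The cost is SAP wording only. The downside is that a favourable within-group p-value can no longer be cited.
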